12.6.2 Microbiome Analyses

Gastrointestinal microbiota data will be summarized descriptively by total counts (per gram of stool sample); by species of aerobic and anaerobic bacteria; and by bacterial resistance to antibiotics (including rifaximin and rifampin).

12.6.3 Safety Analyses

Safety analyses will be descriptive and evaluations will be based on the incidence, intensity and types of treatment-emergent AEs, and changes in clinical laboratory results and vital signs. Concomitant medication will be summarized descriptively. Physical examination findings will be listed. Adverse events will be coded using the MedDRA coding dictionary. Concomitant medications will be coded using the World Health Organization Drug dictionary.

12.6.3.1 Extent of Exposure and Treatment Compliance

Exposure to study drug and treatment compliance will be summarized descriptively.

12.6.3.2 Adverse Events

Adverse events will be coded using the Medical Dictionary for Regulatory Affairs (MedDRA) coding dictionary. Treatment-emergent AEs will be defined as any event with a start date occurring on or after treatment on Day 1.

The incidence of treatment-emergent AEs will be summarized by body system and MedDRA preferred term, overall and by treatment group. If a subject reports the same AE more than once, then that subject will only be counted once for the summary of that AE, using the most severe intensity.

Treatment-emergent AEs will be summarized as follows:

- All treatment-emergent AEs.
- All treatment-emergent AEs by intensity.
- All treatment-emergent AEs by relationship to study drug.
- All treatment-emergent SAEs.
- All treatment-emergent AEs that led to premature discontinuation of study drug.

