6.1 Overview of Study Design

This is a Phase 4, open-label, repeat-dose, parallel-design study in 12 subjects with severe hepatic impairment (MELD 19 to 25 and MELD >25) and 6 healthy subjects with normal hepatic function. At least 6 hepatically impaired subjects will have MELD score >25. Efforts will be made to match subjects across groups in terms of age, weight, and sex. Eligible subjects will complete a Screening Period of up to 21 days prior to dosing (Day 1), a 7-day Treatment Period, and Follow-Up by phone 3 (+1) days later. Subjects will be admitted to the Clinical Research Unit (CRU) on the day prior to the initiation of dosing (Day -1; CRU admission). A plasma sample for PK analysis will be collected on Day 1 prior the first dose. Subjects will receive 550 mg rifaximin BID approximately 12 hour apart for 6 days beginning on Day 1 (Baseline). On Day 7 (End of Treatment; EOT), the final dose of study drug will be administered in the morning following an overnight fast of 10 hours and plasma samples for PK analysis will be collected pre-dose (within 1 hour of the dose) and at 0.25, 0.5, 0.75, 1, 1.5, 2, 4, 6, 8, 10, 12, 16, 20, and 24 hours post-dose. Additionally, a trough blood sample will be collected on Days 2-6, prior to administration of the first daily

Clinical Study Protocol Amendment 1 08Oct2018

dose of rifaximin. Subjects will reside in the CRU for 9 days and will be discharged following the final PK sample collection if safety parameters are acceptable to the Investigator. Each subject will be contacted for a follow-up phone call 3 + 1 days following end of treatment. The study schematic is presented in Figure 1.

Each dose will be administered with a total of 240 mL of water. During the first 4 hours after dose administration, subjects should not lie flat; they should be allowed to sit or stand. Subjects will receive standardized meals while in the CRU.

Subjects will discontinue non-study rifaximin on Day -1 and will only use rifaximin provided as study drug by the sponsor during the Treatment Period. Subjects may resume their prescription rifaximin use following CRU discharge.

Stool samples for microbiome analysis will be collected in the Screening Period and on Day 7 or 8.

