10.1.3 Day 1 (Baseline; pre-dose)

The following procedures will be performed on Day 1 pre-dose:

- Review subject eligibility.
- Assessment of MELD score and Child-Pugh classification (A, B, or C).
- Perform symptom-driven physical exam (general appearance, skin, thorax/lungs, cardiovascular, abdomen, extremities), if necessary.
- Perform pre-dose vital sign assessments (oral temperature, seated blood pressure and pulse). Subjects should be allowed to rest in the seated position for approximately 5 minutes prior to collection of blood pressure and pulse.
- Collect samples for laboratory tests:
 - Blood samples for hematology, chemistry, and coagulation.
 - Blood sample for serum cystatin C.
 - Urine samples for urinalysis and urine drug/nicotine/alcohol screen.

- For females of childbearing potential, blood for a serum pregnancy test and urine for a urine pregnancy test. A negative urine pregnancy test must be confirmed prior to dosing.
- Assess for changes in concomitant medications.
- Assess for pre-dose AEs and SAEs.
- Collect a pre-dose PK blood sample (3 mL in a sodium heparin tube) within 1 hour prior to administration of first daily dose of rifaximin 550 mg.

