11.1 Operating Definitions for Assessing Safety

11.1.1 Adverse Event

An AE is any untoward medical occurrence in a patient or clinical investigation subject administered a study product and which does not necessarily have a causal relationship with the treatment.

An AE can therefore be any unfavorable and unintended sign (that could include a clinically significant abnormal laboratory finding), symptom, or disease temporally associated with the use of a study product, without any judgment about causality (i.e., whether or not considered related to the study product).

Additionally, an event that is associated with study participation (regardless of administration of or relationship to study drug) should be treated as a reportable adverse event for this protocol (e.g., complications resulting from the taking of a blood sample or performance of a protocol required procedure).

An AE **does** include the following:

• Exacerbation or worsening of a pre-existing illness.

NOTE: If the pre-existing illness is the disease under study, then "exacerbation" refers to an unexpected worsening from the condition at baseline.

- Increase in frequency or intensity of a pre-existing episodic event or condition.
- Condition detected or diagnosed after study product administration even though it may have been present prior to the start of the study.
- Symptom associated with disease not previously reported by the subject.

An AE **does not** include the following:

- Medical or surgical procedures (e.g., surgery, endoscopy, tooth extraction, transfusion) as event terms; the condition that led to the procedure is the AE if it meets the definition of an AE.
- Situations where an untoward medical occurrence has not occurred (e.g., hospitalization for cosmetic elective surgery; and social and/or convenience admissions).
- Overdose of either study product or concurrent medication without any signs or symptoms.
- Symptoms associated with disease, which are consistent with the subject's usual clinical course; unless the subject experiences worsening of their symptom(s) or the symptom(s) meet the criteria for an SAE.

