11.1.3 Assessment of Severity

The severity assigned to an AE should be determined by the maximum severity of the AE. The categories described below should be used to estimate the severity of AEs:

- Mild: Transient or mild discomfort; no limitation in activity; no medical intervention/therapy required
- Moderate: Mild to moderate limitation in activity; some assistance may be needed; no or minimal medical intervention/therapy required
- Severe: Marked limitation in activity; some assistance usually required; medical intervention/therapy required; hospitalization or prolongation of current hospitalization possible; may be incapacitating or life threatening

Clinical Study Protocol Amendment 1 08Oct2018

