11.3.1 Time period for Detecting and Reporting of AEs and SAEs

From the time of informed consent through study completion/withdrawal, including the follow-up period.

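### The treatment-emergent AE definition has no worsening clause, so an AE that starts before the first dose and worsens on rifaximin can be left out of the TEAE summaries, depending on how the site records it

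*Combined protocol and SAP*

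**What the plan says.** Section 12.6.3.2 gives the whole definition in one sentence: "Treatment-emergent AEs will be defined as any event with a start date occurring on or after treatment on Day 1". Onset is the only criterion. The same section introduces its planned tables with "Treatment-emergent AEs will be summarized as follows" and names five: all events, by intensity, by relationship to drug, serious events, and events causing early discontinuation of study drug. All five are limited to treatment-emergent events. Section 12.6.3 names no table or listing of AEs that fall outside the definition.

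Collection starts well before dosing. Section 11.3.1 sets the period as "From the time of informed consent through study completion/withdrawal, including the follow-up period", and Section 6.1 says "Eligible subjects will complete a Screening Period of up to 21 days prior to dosing (Day 1), a 7-day Treatment Period". AEs are also checked at Day -1 and, under Section 10.1.3, on Day 1 before the dose ("Assess for pre-dose AEs and SAEs").

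Two other rules affect how a worsening event is recorded. Section 11.1.3 says "The severity assigned to an AE should be determined by the maximum severity of the AE". Section 11.1.1 includes among AEs "Exacerbation or worsening of a pre-existing illness", and likewise a rise in the frequency or intensity of an episodic condition that was already there. For the disease under study, it limits exacerbation to worsening that was not expected.

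**The concern.** A TEAE definition normally has two parts: new events after first dose, and earlier events that get worse after first dose. Only the first is here. The missing part matters when AEs are collected before dosing, as they are in this study, and when the population may have active problems on entry. The impaired subjects have cirrhosis with a MELD score of at least 19, whereas the healthy subjects must be medically normal at Baseline. Any undercount would therefore be expected mainly in the impaired group.

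TEAE incidence is the first safety endpoint in Section 5.4, and Section 4.1 gives the lack of adequate PK and safety data in severe impairment as a reason for the study. With 12 impaired subjects, one case handled differently visibly changes the table. If centers (1 to 3 are planned) record worsening differently, the same clinical course could be counted at one and not at another.

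**Working it through.** There is no planned figure to reproduce. The check applies the rule to one case under both recording practices that the text allows, then works out what one subject is worth.

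**Windows.**
- Pre-dose collection: Day -21 to Day -1, up to 21 days (Sections 6.1, 10.1.1 and 11.3.1).
- Post-dose collection: Day 1 to the follow-up call, 3 (+1) days after Day 7. That is Day 7 + 3 = Day 10 to Day 7 + 4 = Day 11, or 10 to 11 days.

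**Illustrative case.** A mild AE that does not breach any eligibility criterion begins on Day -10, is still present at first dose, and becomes severe on Day 4. The rule is: treatment-emergent if start day is at or after Day 1 treatment.

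| Recording practice | Record(s) | Rule in 12.6.3.2 | Result |
|---|---|---|---|
| One continuing record | start Day -10, severity severe (maximum, 11.1.3) | -10 ≥ 1 is false | in none of the five summaries |
| New record on worsening | start Day -10, mild; start Day 4, severe | 4 ≥ 1 is true for the second record | counted, at severe |

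**Which practice does the protocol require?** Neither is stated.
- *Toward one record:* Section 11.1.3 assigns one severity per AE. Section 11.5 has every AE followed until it resolves or stabilizes. For SAEs, Sections 11.5 and 11.6 send updates to the original form and the matching eCRF entry. Section 11.4 does not mention a new record when severity rises.
- *Toward a new record:* Section 11.1.1 makes worsening of a pre-existing illness or condition an AE. Section 12.6.3.2 also expects repeat reports of one event, and counts the subject a single time at the worst grade.
- *Unsettled:* Section 11.1.1 does not say whether an AE already open from Screening is a pre-existing condition for this purpose, or what start date the worsening takes.

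**Value of one subject.** Incidence changes by 1/n:
- impaired group: 1/12 = 8.3 percentage points
- healthy group: 1/6 = 16.7 points
- all subjects: 1/18 = 5.6 points

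**After the change.** With a worsening clause the Day 4 event meets the definition under either practice. Applying it to a single record requires the date of the increase. The protocol does not ask for that date, so the clause needs a recording instruction alongside it.

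**The case against.** The strongest reply is that Section 11.1.1 already solves the problem: worsening is an AE in its own right, so a Day 4 worsening has a Day 4 start date and is counted. For problems present at consent and recorded as medical history, this largely stands. It is less complete for cirrhosis itself, where only unexpected worsening qualifies. It does not settle what happens to an AE that arose between consent and first dose and is already open.

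That leaves a narrow group, and Section 7.1.2 narrows it further by excluding acute illness within 1 week of admission, with eligibility reviewed again on Day -1 and Day 1. The safety analysis is descriptive and the primary objective is pharmacokinetic. Section 12 also assigns data-handling conventions to a detailed SAP, which is not in the text reviewed and could close the gap. These points limit the importance of the issue, but they do not supply the missing rule.

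A reader might infer more than the documents support:
- *That every such event is lost.* Exclusion follows only if the worsening stays on the original record, and no section requires that.
- *That all safety output is affected.* The laboratory summaries and shifts (12.6.3.3) and vital signs (12.6.3.4) do not use the TEAE definition. AEs are still recorded from consent, and SAEs are reported within 24 hours whatever their start date. The synopsis separately tabulates reasons for discontinuing treatment.
- *That AEs found on Day 1 before dosing would be counted.* The definition is anchored to treatment on Day 1, not to the calendar day; pre-dose events are assessed as a separate step, and actual dose time is recorded.

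**Conclusion.** The gap is real and conditional. The TEAE definition has no worsening clause and the protocol sets no recording convention, so an AE that begins between consent and first dose and worsens on rifaximin can be absent from all five TEAE summaries, depending on site practice.

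Each such subject is worth 8.3 points of TEAE incidence in the 12 impaired subjects. This assumes full enrollment and that the by-group tables separate impaired from healthy subjects. The documents give no rate of ongoing Screening AEs or of worsening, so no expected total loss can be stated. That the loss would fall mainly on the impaired group is a reasonable expectation from the eligibility criteria, not something the documents quantify.

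The issue does not touch the PK analysis. It is worth correcting because TEAE incidence is a stated safety endpoint and the correction is simple.

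**What to change.** In Section 12.6.3.2, and in the SAP, define a TEAE as an AE that starts at or after the first dose through follow-up, or that started earlier and increases in severity or becomes serious at or after the first dose through follow-up.

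Add a CRF completion instruction, with a matching line in Section 11.4: when an AE that began before the first dose worsens afterward, record the worsening as a new AE with its own start date and severity. The original record then keeps its pre-dose severity, and every center handles the case in the same way.

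The cost is one sentence in the protocol and SAP and one CRF instruction. The downside is that reported TEAE counts may be slightly higher. The existing once-per-subject counting rule prevents double counting of the same AE in a subject.

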Exploratory: To assess the effect of rifaximin administration on the intestinal microbiome in subjects with severe hepatic impairment (MELD 19 to 25 and MELD >25).

Methodology:

This is a Phase 4, open-label, repeat-dose, parallel-design study in 12 subjects with severe hepatic impairment (MELD 19 to 25 and MELD >25) and 6 healthy subjects with normal hepatic function. At least 6 of the hepatically impaired subjects will have MELD score >25. Efforts will be made to match subjects across groups in terms of age, weight, and sex. Eligible subjects will complete a Screening Period of up to 21 days prior to dosing (Day 1), a 7-day Treatment Period, and Follow-Up by phone 3 (+1) days later. Subjects will be admitted to the Clinical Research Unit (CRU) on the day prior to initiation of dosing (Day -1; CRU admission). A plasma sample for PK analysis will be collected on Day 1 prior to the first dose. Subjects will receive 550 mg rifaximin BID approximately 12 hours apart for 6 days beginning on Day 1 (Baseline). On Day 7 (End of Treatment; EOT), the final dose of study drug will be administered in the morning following an overnight fast of 10 hours. Plasma samples for PK analysis will be collected pre-dose (within 1 hour of the dose) and at 0.25, 0.5, 0.75, 1, 1.5, 2, 4, 6, 8, 10, 12, 16, 20, and 24 hours post-dose. Additionally, a trough blood sample will be collected on Days 2-6, prior to administration of the first daily dose of rifaximin. Subjects will reside in the CRU for 9 days and will be discharged following the final PK sample collection if safety parameters are acceptable to the Investigator. Each subject will be contacted for a follow-up phone call on 3 (+1) Days following end of treatment.

Number of patients planned: N = 18, 12 subjects with liver impairment and 6 matched healthy volunteer subjects. At least 6 of the hepatic impaired subjects will have a MELD score of >25.

Diagnosis and main criteria for inclusion:

Hepatically impaired subjects will be ≥ 18 years of age, have a diagnosis of liver cirrhosis and a MELD score of ≥ 19 at Screening. Note: At least 6 of the hepatically impaired subjects will have a MELD score of ≥ 25 .

Key exclusion criteria:

Subject has known allergy to rifaximin, rifampin, or other rifamycins, excipients and/or vehicles used in the formulation, or any other clinically significant allergies.

Subject has participated in an investigational drug or device study within 30 days prior to Day 1 (Baseline).

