11.1.4 Assessment of Causality

The investigator should assess the relationship of the AE, if any, to the study drug using the following definitions:

Related: Event or laboratory test abnormality with reasonable time relationship to drug intake. Cannot be attributed to disease or other drugs. Response to withdrawal is clinically reasonable and re-challenge is not required.

Probable: Event or laboratory test abnormality with reasonable time relationship to drug intake. Unlikely to be attributed to disease or other drugs. Response to withdrawal is clinically reasonable and re-challenge is not required.

Possible: Event or laboratory test abnormality with reasonable time relationship to drug intake. Could also be explained by disease or other drugs. Information on drug withdrawal may be lacking or unclear.

Unlikely: Event or laboratory test abnormality with a time to drug intake that makes a relationship improbable (but not impossible). Disease or other drugs provide plausible explanations.

Not Related: Event or laboratory test abnormality with a time to drug intake that makes a relationship implausible. Disease or other drugs provide plausible explanations.

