11.9 Regulatory Reporting Requirements for SAEs

The investigator, or responsible person per local requirements, must comply with the applicable local regulatory requirements related to the reporting of SAEs and IND safety reports to regulatory authorities and their IRB.

12 Statistics

A detailed statistical analysis plan (SAP) will be prepared for this study. The plan will contain a discussion of the statistical methods, a description of the computational algorithms and data handling conventions, and specifications for the data summaries and listings. It will be finalized before database lock.

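### The repeat-AE rule in Section 12.6.3.2 selects on intensity only, so the by-relationship table can show less than the strongest relationship assigned

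*Combined protocol and SAP*

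**What the plan says.** Section 12.6.3.2 (Adverse Events) plans incidence tables by body system and preferred term. The rule for repeats opens "If a subject reports the same AE more than once" and continues "that subject will only be counted once for the summary of that AE, using the most severe intensity". The section then lists five summaries of treatment-emergent events. Two matter here: "All treatment-emergent AEs by intensity" and "All treatment-emergent AEs by relationship to study drug". Neither carries a selection rule of its own.

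The two attributes are judged separately. Section 11.1.3 defines three intensity levels (Mild, Moderate, Severe) and says "The severity assigned to an AE should be determined by the maximum severity of the AE". Section 11.1.4 defines five relationship levels (Related, Probable, Possible, Unlikely, Not Related), introduced by "The investigator should assess the relationship of the AE, if any, to the study drug using the following definitions".

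The opening paragraph of Section 12 adds "A detailed statistical analysis plan (SAP) will be prepared for this study". It says that this plan will cover data-handling conventions and be final before database lock. The Synopsis gives the planned size as "N = 18, 12 subjects with liver impairment and 6 matched healthy volunteer subjects".

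**The concern.** Counting a subject once at the worst intensity is the natural convention for an intensity table. It does not carry over to a relationship table, because the most severe occurrence need not be the one most strongly linked to the drug. Take a subject with a mild headache judged Related and a later severe headache judged Not Related. Sorted on intensity, that subject enters the by-relationship table as Not Related.

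The direction is fixed. The level kept belongs to one of the occurrences, so it cannot exceed the strongest level among them; it can only equal it or fall below it. At stake is the reading of a single table, the one a reader would consult to see how many subjects had an event considered possibly drug-related or more. If the rule was meant for the by-intensity table alone, the by-relationship table has no rule for repeats, and the choice falls to whoever programs it.

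**Working it through.** The plan states no figure on this point, so there is nothing to reproduce. The check is whether the rule, read literally, gives a determinate and conservative relationship.

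**Inputs**
- Intensity: 3 levels (Section 11.1.3).
- Relationship: 5 levels (Section 11.1.4).
- Selection: the occurrence with the highest intensity (Section 12.6.3.2).
- Group sizes: 12 impaired, 6 healthy, 18 in all (Synopsis).

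**Step 1: list the patterns.** One occurrence has 3 × 5 = 15 possible intensity-relationship combinations. Two occurrences of the same event give 15 × 15 = 225 ordered patterns. These are counts of what can happen, not probabilities.

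**Step 2: sort the patterns by what the rule does.**

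| Pattern | Count | Relationship shown |
|---|---|---|
| Intensities differ; the more severe occurrence has the weaker relationship | 6 × 10 = 60 | Weaker than the strongest assigned |
| Intensities differ; the more severe occurrence has the same or a stronger relationship | 6 × 15 = 90 | Equal to the strongest assigned |
| Intensities equal; relationships differ | 3 × 20 = 60 | Not determined by the rule |
| Intensities equal; relationships equal | 3 × 5 = 15 | No conflict |
| Total | 225 | |

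The 6 is the number of ordered pairs of different intensities (3 × 2). Of the 25 ordered relationship pairs, 10 have the selected occurrence weaker, 15 have it equal or stronger, and 20 have the two unequal.

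**Step 3: count those that cross the line a reader would draw.** Among the 60 understated patterns, the subject appears as Unlikely or Not Related while the other occurrence was judged Possible, Probable or Related in 6 × (2 × 3) = 36.

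**Step 4: check the direction.** In no pattern is the level shown stronger than the strongest level assigned.

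**Step 5: apply the alternative rule.** If the by-relationship table takes the strongest relationship per subject and preferred term, 0 of the 225 patterns are understated and 0 are undetermined.

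**Step 6: size per affected subject.** 1/12 = 8.3 percentage points of the impaired group and 1/18 = 5.6 points overall.

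The number of subjects affected cannot be worked out. It needs the rate at which the same event recurs in a subject and the joint distribution of intensity and relationship across recurrences. The documents give neither.

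**The case against.** The case for leaving the text alone has several parts.

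- **The rule may not reach the by-relationship table.** It can be read as two instructions, count once and grade intensity at its worst, with nothing said about relationship. A reader might infer that the protocol prescribes the intensity sort in every table; it does not say so. This stands as a point about wording. It does not remove the gap, since on the narrower reading the by-relationship table has no rule for repeats.
- **The later analysis plan may settle it.** Section 12 promises one, and its text is not among the documents. This also stands: the final plan cannot be said to lack the rule. But an analysis plan that copied Section 12.6.3.2 would carry the problem forward.
- **Nothing false is reported.** A reader might infer that the table would show a relationship the investigator never gave. It would not: the level shown was assigned, to the most severe occurrence. The accurate statement is that it can be weaker than the strongest level assigned to any occurrence.
- **Nothing disappears.** A reader might infer that drug-related events would be hidden. The event still appears in the all-event and by-intensity tables. Section 11.4 requires every event to be assessed and recorded, and serious events are documented with a causality assessment.
- **Safety is not the study's main purpose.** Section 4.1 notes that both PK and safety data are lacking at MELD 19 and above, but says the study is run to provide PK data. Section 5.1 states a PK objective only. Event incidence is a safety endpoint in Section 5.4; relationship is not named there, nor among the bases for safety evaluation in Section 12.6.3.
- **Repeats may be few.** Dosing is 13 doses over 7 days (6 × 2 + 1), with a telephone call 3 (+1) days after the end of treatment. Section 11.1.3 grades an event at its maximum, so one fluctuating event need not become two records.

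These points limit the importance of the matter. None supplies the missing rule.

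**Conclusion.** The point holds as a minor one. Read literally, the only repeat-event rule in Section 12.6.3.2 makes the by-relationship table report the relationship of the most severe occurrence. That can match or understate the strongest relationship assigned, never overstate it, and it leaves ties in intensity open. The effect is confined to one descriptive safety table; the PK analyses and the sample size are untouched. One affected subject is 8.3 percentage points of the 12 impaired subjects. The conclusion assumes that the unrestricted rule is applied to all the listed summaries and that the later analysis plan adds no rule of its own.

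Three stronger conclusions might be inferred and are not supported:

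- **A probability of understatement.** The pattern counts would become one only if the levels were uniform and independent, and a repeat would have to occur first. The documents support neither assumption and give no repeat rate.
- **A systematic tendency to attribute severe recurrences to liver disease.** The definitions in Section 11.1.4 make this conceivable, since they weigh disease as an alternative explanation, but no figure shows it.
- **An effect of 1/6 = 16.7 points in a MELD stratum.** Section 12.6.3.2 plans event tables overall and by treatment group, and does not specify MELD strata.

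**What to change.** In Section 12.6.3.2, and in the analysis plan before database lock, tie the most-severe-intensity rule to the by-intensity table. Then add one sentence, for example: In the by-relationship summary, each subject is counted once per preferred term at the strongest relationship assigned to any occurrence (Related > Probable > Possible > Unlikely > Not Related).

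This also resolves occurrences of equal intensity. The cost is one sentence and one sort order in the table program, with no change to study conduct, data collection or the PK analyses. The downside is that the by-relationship table may show slightly more drug-related events than a table sorted on intensity.
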